## Appendix 5. Toxicity Table

**National Institute of Allergy and Infectious Diseases, Division of Microbiology and Infectious Diseases (DMID) Pediatric Toxicity Tables (2007) and Division of AIDS Table for Grading the Severity of Adult and Pediatric Adverse Events (2017)**

### **ABBREVIATIONS USED IN FOLLOWING TABLES:**

Abbreviation/ Term	Definition/Explanation
ALT	alanine aminotransferase
aPTT	activated partial thromboplastin time
AST	aspartate aminotransferase
AV block	atrioventricular block
bpm	beats per minute
BUN	blood urea nitrogen
CK	creatinine kinase
CPK	creatine phosphokinase
FEV 1	forced expiratory volume in 1 second
G	Gram
HI	High
HPF	high power field
IU	international unit
IV	Intravenous
K/CUMM	$\times 10^3/\text{mm}^3$
LLN	lower limit of normal

Abbreviation/ Term	Definition/Explanation
LO	Low
mEq	Milliequivalent
mmHg	millimeter of mercury
[name]
N	Normal
PT	prothrombin time
PTT	partial thromboplastin time
QTc	QT-interval corrected for heart rate
QTcB	Bazett's corrected QT interval
QTcF	Fridericia's corrected QT interval
RBC	red blood cell
Rx	Therapy
S	Second
TBV	Total Blood Volume
U	Unit
ULN	upper limit of normal

### **ESTIMATING SEVERITY GRADE**

For abnormalities NOT found elsewhere in the Toxicity Tables use the scale below to estimate grade of severity:

**GRADE 1      Mild:** Transient or mild discomfort (<48 hours); no medical intervention/therapy required

**GRADE 2      Moderate:** Mild to moderate limitation in activity - some assistance may be needed; no or minimal medical intervention/therapy required

**GRADE 3      Severe:** Marked limitation in activity, some assistance usually required; medical intervention/therapy required hospitalizations possible.

### **LABORATORY RANGES**

Where discrepancies in the ULN and LLN of laboratory ranges occur between those included in this document and those of the laboratory that performs the assays, the values provided by the laboratory will be used for assignment of severity grade.

**CLINICAL ADVERSE EVENTS**

Cardiovascular	Mild (Grade 1)	Moderate (Grade 2)	Severe (Grade 3)
Arrhythmia		Asymptomatic, transient signs, no Rx required	Recurrent/persistent; symptomatic Rx required
Hemorrhage, blood loss	Estimated blood loss $\leq$ 25% of Total Blood Volume (TBV)	Estimated blood loss $>$ 25% TBV, symptomatic, no transfusion required	Transfusion required
QTcF (Fridericia's correction) a or QTcB (Bazett's correction)	Asymptomatic, QTc interval 450-479 ms, OR Increase in interval $<$ 30 ms above baseline	Asymptomatic, QTc interval 480-499 ms, OR Increase in interval 30-59 ms above baseline	Asymptomatic, QTc interval $\geq$ 500 ms, OR Increase in interval $\geq$ 60 ms above baseline
PR interval (prolonged)	1st degree AV block (PR interval $>$ normal for age and rate)	Type I 2 nd degree AV block	Type II 2 nd degree AV block OR Ventricular pause $>$ 3.0 s
Respiratory	Mild (Grade 1)	Moderate (Grade 2)	Severe (Grade 3)
Cough	Transient-no treatment	Persistent cough	Interferes with daily activities
Bronchospasm, acute	Transient wheeze; no treatment;	Requires treatment; normalizes with bronchodilator and $FEV_1 < 80\%$ predicted before bronchodilator	Minimal normalization with bronchodilator and $FEV_1 < 80\%$ predicted after bronchodilator
Dyspnea	Does not interfere with usual and social activities	Interferes with usual and social activities, no treatment	Prevents daily and usual social activity or requires treatment
Nasal discharge (rhinitis infective per CTCAE 4.0)	-	Localized; local intervention indicated (e.g. topical antibiotic, antifungal, or antiviral)	-
Pharyngitis (CTCAE 4.0)	-	Localized; local intervention indicated (e.g. topical antibiotic, antifungal, or antiviral)	IV antibiotic, antifungal, or antiviral intervention indicated; radiologic or operative intervention indicated
Pneumonitis (rales or rhonchi) (CTCAE 4.0)	Asymptomatic; clinical or diagnostic observations only; intervention not indicated	Symptomatic; medical intervention indicated; limiting instrumental ADL	Severe symptoms; limiting self-care ADL; oxygen indicated

a Inclusion dependent upon protocol requirements

Respiratory (continued)	Mild (Grade 1)	Moderate (Grade 2)	Severe (Grade 3)
Lung infection (CTCAE 4.0)	-	Moderate symptoms; oral intervention indicated (e.g. antibiotic, antifungal, antiviral)	IV antibiotic, antifungal, or antiviral intervention indicated; radiologic, endoscopic, or operative intervention indicated
Gastrointestinal	Mild (Grade 1)	Moderate (Grade 2)	Severe (Grade 3)
Nausea	No interference with activity	Some interference with activity	Prevents daily activities
Vomiting	No interference with activity or 1-2 episodes/24 hours	Some interference with activity or >2 episodes/24 hours	Prevents daily activity or requires IV hydration
Diarrhea	2-3 loose or watery stools or <400 g/24 hours	4-5 loose or watery stools or 400-800 g/24 hours, mild dehydration	6 or more loose or watery stools or >800 g/24 hours or requires IV hydration
Urinary Tract	Mild (Grade 1)	Moderate (Grade 2)	Severe (Grade 3)
Urinary tract infection (CTCAE 4.0)	-	Localized; local intervention indicated (e.g., oral or topical antibiotic, antifungal, antiviral)	IV antibiotic, antifungal, or antiviral intervention indicated; radiologic or operative intervention indicated
Reactogenicity	Mild (Grade 1)	Moderate (Grade 2)	Severe (Grade 3)
Local reactions			
Pain	Does not interfere with activity	Repeated use of non-narcotic pain reliever >24 hours or interferes with activity	Any use of narcotic pain reliever or prevents daily activity
Tenderness	Discomfort only to touch	Discomfort with movement	Significant discomfort at rest
Erythema/redness b	≤ 2.5 cm	>2.5 cm with < 50% surface area of the segment area involved 5.1-10 cm	>10 cm
Induration/swelling c	≤ 2.5cm and does not interfere with activity	>2.5 cm with < 50% surface area of the segment area involved or interferes with activity	>10 cm or prevents daily activity

b In addition to grading the measured local reaction at the greatest single diameter, the measurement should be recorded as a continuous variable.

c Induration/swelling should be evaluated and graded using the functional scale as well as the actual measurement.

Reactogenicity (continued)	Mild (Grade 1)	Moderate (Grade 2)	Severe (Grade 3)
Systemic reactions			
Allergic reaction	Pruritus without rash	Localized urticaria	Generalized urticaria; angioedema or anaphylaxis
Headache	No interference with activity	Repeated use of non-narcotic pain reliever >24 hours or some interference with activity	Significant; any use of narcotic pain reliever or prevents daily activity
Fatigue	No interference with activity	Some interference with activity	Significant; prevents daily activity
Myalgia	No interference with activity	Some interference with activity	Significant; prevents daily activity
All Other Conditions	Mild (Grade 1)	Moderate (Grade 2)	Severe (Grade 3)
Illness or clinical adverse event (as defined according to applicable regulations)	No interference with activity	Some interference with activity not requiring medical intervention	Prevents daily activity and requires medical intervention
Unintentional Weight Loss	-	5 to <9% loss in body weight from baselines	≥9 to 20% loss in body weight from baseline
Underweight	-	WHO BMI or weight-for-height z-score < -2 to -3	WHO BMI or weight-for-height z-score < -3

**LABORATORY AND VITAL SIGNS TOXICITY GRADING (Some laboratory values have been modified to be consistent with the normal ranges of the laboratory used in the present study)**

Blood, Serum, or Plasma Chemistries a	LO/HI/N b	Mild (Grade 1) c	Moderate (Grade 2)	Severe (Grade 3)
Sodium (mEq/L or mmol/L)	LO	131-<LLN	130	<130
	HI	>ULN-148	149-150	>150
Potassium (mEq/L or mmol/L)	LO	<LLN-3.0	<3.0-2.5	<2.5
	HI	>ULN-6.0	>6.0-6.5	>6.5
Glucose (mmol/L)	LO	<LLN-3.0	<3.0-2.2	<2.2
	HI	>ULN-8.9	>8.9-13.9	>13.9
Blood urea nitrogen (mmol/L)	HI	>8.9-17.8	>17.8-35.5	>35.5
Creatinine (mg/dL)	HI	0.7-1.0 x ULN	1.1-1.6 x ULN	1.7-2.0 x ULN
Calcium (mmol/L) (CTCAE 4.0)	LO	<LLN-2.0	<2.0-1.75	<1.75
	HI	>ULN-2.9	>2.9-3.1	>3.1
Magnesium (mmol/L) (CTCAE 4.0)	LO	1.2-1.4	0.9-1.1	0.6-<0.9
Phosphate (mmol/L) (CTCAE 4.0)	LO	3.0-<3.5	2.5-<3.0	1.5-<2.5
Creatine kinase (CPK or CK) (CTCAE 4.0)	HI	>ULN-2.5xULN	>2.5xULN-5xULN	>5xULN
Albumin (g/L)	LO	<30-28	<28-25	<25
Total protein (g/L)	LO	<LLN-52	<52-50	<50
Alkaline phosphatase (U/L) (CTCAE 4.0)	HI	>ULN-2.5xULN	>2.5xULN-5xULN	>5xULN
AST (U/L) (CTCAE 4.0)	HI	>ULN-3xULN	>3xULN-5xULN	>5xULN
ALT (U/L) (CTCAE 4.0)	HI	>ULN-3xULN	>3xULN-5xULN	>5xULN

Blood, Serum, or Plasma Chemistries a	LO/HI/N b	Mild (Grade 1) c	Moderate (Grade 2)	Severe (Grade 3)
Bilirubin, serum total (mmol/L) (CTCAE 4.0)	HI mmol/L	>ULN-1.5xULN	>1.5xULN-3xULN	>3xULN
Bilirubin, serum direct (mmol/L) (CTCAE 4.0)	HI mmol/L	>ULN-1.5xULN	>1.5xULN-3xULN	>3xULN
Amylase (U/L) (CTCAE 4.0)	HI	>ULN-1.5xULN	>1.5xULN-2xULN	>2xULN
Lipase (U/L) (CTCAE 4.0)	HI	>ULN-1.5xULN	>1.5xULN-2xULN	>2xULN
Uric acid (mg/dL) (CTCAE 4.0)	HI	>ULN – 10.0 without physiologic consequences	10.0-<12.5	>12.5 with physiologic consequences

a Depending upon the laboratory used, references ranges, eligibility ranges and grading may be split out by sex and/or age.

b Low, High, Not Graded (N).

c If initial boundary of grade 1 has gap from reference range or eligibility range, calculations based on the New England Journal of Medicine (NEJM) reference ranges.

Hematology	LO/HI/N a	Mild (Grade 1) b	Moderate (Grade 2)	Severe (Grade 3)
Hemoglobin (g/dL)	LO	9.5-10.4	8.5-<9.5	<8.5
White blood cell count (K/CUMM)	HI	11.00-15.00	15.00-20.00	>20.00
	LO	2.50-3.50	1.50-2.49	<1.50
Lymphocytes (K/CUMM)	LO	0.76-0.90	0.50-0.75	<0.5
Neutrophils (K/CUMM)	LO	1.50-1.95	1.00-1.49	<1.00
Eosinophils (K/CUMM)	HI	0.58-0.74	0.75-1.50	>1.50
Platelets (K/CUMM)	LO	<125-100	100-50	<50
Coagulation				
Prothrombin time (PT, seconds)	HI	1.1-1.2 xULN	1.3-1.5 x ULN	1.6 -3.0 x ULN
Partial thromboplastin time (PTT or aPTT, seconds)	HI	1.1-1.6 x ULN	1.7-2.3 x ULN	2.4-3.0 x ULN
Fibrinogen (mg/dL) (CTCAE 4.0)	HI	>ULN-500	501-600	>600
	LO	<LLN-0.75xLLN	<0.75xLLN-0.5xLLN	<0.5xLLN
Urine				
Protein (dipstick)	HI	1+	2+	>2+
Glucose (dipstick)	HI	1+	2+	>2+
Blood (microscopic) - red blood cells per high power field (RBC/HPF)	HI	5-10	11-50	>50 and/or gross blood

a Low, High, Not Graded.

b If initial boundary of grade 1 has gap from reference range or eligibility range, calculations based on the New England Journal of Medicine (NEJM) reference ranges.

Vital Signs	LO/HI/N a	Mild (Grade 1) b	Moderate (Grade 2)	Severe (Grade 3)
Fever (°C) c	HI	38.0-38.4	38.5-38.9	>38.9
Fever (°F)	HI	100.4-101.1	101.2-102.0	>102.1
Tachycardia (>6 years) - beats per minute	HI	101-115	116-130	>130 or ventricular dysrhythmias
Tachycardia (≤6 years) - beats per minute		120-130	131-150	>150 or ventricular dysrhythmias
Bradycardia - beats per minute	LO	<60-50 and no symptoms	<60-50 with symptoms	<50
Hypertension (systolic) - mm Hg d	HI	>90-95 th percentile adjusted for age, height, and gender	≥95-99 th percentile adjusted for age, height, and gender	≥99 th percentile adjusted for age, height, and gender
Hypertension (diastolic) - mm Hg	HI	>90-95 th percentile adjusted for age, height, and gender	≥95-99 th percentile adjusted for age, height, and gender	≥99 th percentile adjusted for age, height, and gender
Hypotension (systolic) - mm Hg	LO	85-89	80-84	<80
Tachypnea - breaths per minute	HI	31-35	36-40	>40

a Low, High, Not Graded.

b If initial boundary of grade 1 has gap from reference range or eligibility range, calculations based on the New England Journal of Medicine (NEJM) reference ranges.

c Oral temperature; no recent hot or cold beverages or smoking. A protocol should select either °C or °F for inclusion.

d Assuming subject is awake, resting, and supine; for adverse events, 3 measurements on the same arm with concordant results.

## **Appendix 6. COVID-19 Study Site Guidance**

### **BACKGROUND**

As the impact of coronavirus disease 2019 (COVID-19) continues to develop, Paidion Research Inc. and Arcutis Biotherapeutics Inc. have collated the following guidelines for study sites participating in the ARQ-151-215 study. While it is ideal for subjects to perform all protocol-specific assessments at the study site, both Paidion and Arcutis are focused on prioritizing subject safety and data integrity. Therefore, the following guidelines will identify challenges and mitigation strategies while operating clinical trials remotely.

### **REMOTE DATA COLLECTION**

In the event subjects are unable to complete protocol-specific assessments onsite, study sites may collect data from subjects remotely via telephone and/or by traditional mail or email. The method used for data collection must be clearly documented in the source. Whenever possible, sites should adhere to the protocol visit window for remote data collection. Screening and Baseline (Day 1) visits/assessments must be performed in the clinic and must NOT be completed remotely. If necessary, these visits can be delayed ensuring they are conducted in the clinic and not remotely.

Data collection by phone may be performed. Subjects are contacted via telephone and site staff will collect data verbally for all critical data points applicable. Subject responses should be recorded in the site source documents. Data collected remotely should be entered into the EDC system.

Data collection by mail or email may also be performed for applicable assessments. Site staff will contact subjects via traditional mail or email to collect data using paper versions of study questionnaires.

Investigator assessments and subject questionnaires normally completed during on-site visits should be completed on the appropriate paper source documents and entered in the EDC. The following subject assessments/questionnaires are approved to be collected via telemedicine/remote:

- WI-NRS
- CDLQI
- CDI-2
- Subject Local Tolerability
- Adverse Events
- Concomitant medication
- Review of Subject Diary

The following Investigator assessments cannot be completed via telemedicine/remote:

- IGA, I-IGA
- PASI
- BSA
- Investigator Local Tolerability
- Subject Weight

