- d BSA, IGA affected by plaque psoriasis will be determined to qualify for study entry (Screening and Baseline) and will be measured at the Week 2 and Week 4 visits. Scalp, palms and soles should be excluded from consideration in these assessments. Additionally, Intertriginous Area-IGA (I-IGA), PASI, and WI-NRS will be evaluated. WI-NRS pruritus assessment will be completed by subjects  $\geq$  8 years old, or by parent/caregiver for subjects  $<$  8 years old. All other assessments will be performed by the Investigator or study staff, as appropriate.
- e Local tolerability assessments should be recorded prior to study drug application for the Investigator assessment of skin irritation (Berger and Bowman skin irritation score) and 10-15 minutes post-drug application for the subject's '0-3' burning/stinging assessment (subject-rating completed by the subject or parent/caregiver). At the Week 4 visit, only the Investigator assessment of skin irritation will be performed. Note for investigator tolerability assessments: reactions at the site of product IP application, which may occur post-Baseline, should be differentiated from the preexisting inflammation associated with the subject's psoriasis.
- f For females that have started menstruation, a serum pregnancy test will be performed during Screening. A urine pregnancy test will be administered to all females of child-bearing potential. A negative result is required for continued participation in the study, and results must be available prior to dispensing of study drug
- g All enrolled subjects will have a trough PK sample collected at the Week 4 visit. A subset of 6 subjects who consent will provide an additional PK sample pre-dose (within 1 hour) at the Week 2 visit.
- h Subjects/caregiver to apply assigned IP in clinic at Baseline and Week 2. All Investigator assessments should be completed prior to IP application.
- i The number of kits to be dispensed is based on %BSA affected. See IP Handling Manual for details. Site should review IP kit to ensure sufficient IP is available until the next visit and only dispense additional IP if needed.
- j Every tube should be weighed and recorded when dispensed and returned.
- k Any emergent AEs will be followed in the clinic for up to 1 month at the Investigator's discretion until resolved or otherwise judged as clinically stable.

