### **5.2 Study Endpoints**

#### **5.2.1 Primary Endpoints**

The primary endpoints will be PK, safety and tolerability.

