- All subjects should apply medication each evening (except on clinic visit days) at least 15 minutes after showering or bathing (if they take an evening shower/bath) and then not wash areas where ARQ-151 cream has been applied until at least 4 hours after study drug application and preferably not until the following morning. Investigational product should be applied at least 20 minutes before going to bed.
- Subjects should maintain treatment of areas with study drug for the duration of the study regardless of whether treatable areas of psoriasis clear prior to Week 4 visit.

New lesions that develop during the study should be treated (except scalp). An unscheduled visit is not required for starting treatment of new lesions.

Each investigational product tube will be weighed prior to dispensing at the Baseline visit and at subsequent visits. Investigational product tubes must be returned by subjects at each study visit, both empty and full, and will be weighed. If the subject’s actual use is substantially different than the expected use for the subject’s BSA, the subject/parent/caregiver will be retrained on the study drug application technique.

At the final clinic visit, the subject should return all IP (used or unused), the digital scale, and any remaining plastic dishes.

Refer to the Investigational Product (IP) Handling Plan for detailed instructions.

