### Subject Local Tolerability Assessment will be performed as follows:

- Baseline, Week 2

This assessment will be administered by the site 10 to 15 minutes after study drug application in the clinic at Baseline and at Week 2. Response may be by the subject and/or parent/caregiver, as deemed appropriate by the Investigator.

Grade	Sensation Following Drug Application
0 (none)	No sensation
1 (mild)	Slight warm, tingling sensation; not really bothersome
2 (moderate)	Definite warm, tingling sensation that is somewhat bothersome
3 (severe)	Hot, tingling/stinging sensation that has caused definite discomfort

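### Appendix 6 allows the subject burning/stinging score to be collected remotely without its 10 to 15 minute timing, so the Week 2 column can mix immediate and later ratings

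*Protocol*

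**What the plan says.** Protocol 7.1.7 says of the subject's sensation score: "This assessment will be administered by the site 10 to 15 minutes after study drug application in the clinic", with Baseline and Week 2 as the time points. SAP 10.3 repeats this. Footnote e to the Protocol schedule gives the same 10 to 15 minute interval and adds: "At the Week 4 visit, only the Investigator assessment of skin irritation will be performed".

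Appendix 6 (Remote Data Collection) says that, when on-site assessment is not possible, "study sites may collect data from subjects remotely via telephone and/or by traditional mail or email". It then states "The following subject assessments/questionnaires are approved to be collected via telemedicine/remote" and lists seven items, one of which is Subject Local Tolerability. On postal routes it says only: "Data collection by mail or email may also be performed for applicable assessments". It does not say which assessments those are. Screening and Baseline may not be remote.

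Protocol 6.9.2 puts application in the clinic on clinic visit days and in the evening at home on all others. Protocol 5.2.1 states: "The primary endpoints will be PK, safety and tolerability".

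SAP 10.3 plans one summary of the subject score at Baseline and Week 2. It does not refer to mode of collection or to time since application.

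**The concern.** The score measures a sensation within minutes of a dose. The other rating scales on the remote list carry their own recall periods: 24 hours for WI-NRS, one week for CDLQI and two weeks for CDI-2. A telephone call or a paper form does not change what those scales measure. For the burning/stinging score, a rating given hours later is a different measurement.

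If Week 2 is remote, no application takes place in the clinic, and 6.9.2 then puts that day's dose in the evening at home. A daytime contact would normally refer to an earlier application. Such a rating could enter the same Week 2 column as ratings taken on time, while every Baseline rating was taken on time in the clinic. A reader comparing the two columns could not tell a change in tolerability from a change in how the score was obtained.

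**Working it through.** The plan gives no figure for this point, so there is none to reproduce. The check has two parts: a comparison of the texts, then an illustration of size.

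**Which ratings are exposed**

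- Baseline: must be in the clinic (Appendix 6). Not exposed.
- Week 2: subject rating due (Protocol 7.1.7), and remote collection allowed (Appendix 6). Exposed.
- Week 4: no subject rating (schedule footnote e). Not exposed.

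**Whether another rule closes the gap**

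- SAP 8.4 assigns unscheduled assessments to visits by date and time. It sets no window after application.
- SAP 8.3.1 plans a listing of subjects affected by COVID-19. Its stated fields do not include mode or time of assessment.
- Appendix 6 requires the collection method to be documented in source, but no analysis uses it.
- The Investigator irritation score cannot be done remotely (Appendix 6). On a remote Week 2 contact, the subject score would be that child's only tolerability scale.
- Under Protocol 7.7.1, application site reactions count as adverse events only when they lead to intervention, suspension or discontinuation. Milder burning need not be recorded there.

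**Size, on assumed values**

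From the documents: N is about 20 (Protocol 8.1.3). Each child is 100/20 = 5 percentage points if all 20 are rated.

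Assumed, because the documents do not give them:

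- p, the true share reporting any sensation at 10 to 15 minutes;
- k, the number of Week 2 ratings taken by later recall;
- s, the ratio of the recalled rate to the immediate rate. Below 1 means under-reporting, above 1 over-reporting.

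Expected Week 2 rate = [(N − k)p + k·p·s]/N, so the change is p(s − 1)k/N.

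| p | k | s = 0 | s = 0.5 | s = 1.5 |
|---|---|---|---|---|
| 5% | 2 | 4.5% | 4.75% | 5.25% |
| 10% | 4 | 8.0% | 9.0% | 11.0% |
| 20% | 6 | 14.0% | 17.0% | 23.0% |

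For example, with p = 10%, k = 4 and s = 0.5: (16 × 0.10 + 4 × 0.05)/20 = 1.8/20 = 9.0%.

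The largest shift shown is 0.20 × 6/20 = 6 points, slightly more than one child. With k = 0 there is no shift.

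**The case against.** The strongest reply is that Appendix 6 changes where an assessment is done and does not waive its timing. Its guidelines say that procedures are to follow the protocol where that is possible. A call 10 to 15 minutes after the evening dose would meet footnote e, and 6.9.2 has the cream applied at least 20 minutes before bed, so such a call is feasible. The sponsor would rather delay a clinic visit than replace it, and COVID-19 deviations are to be distinguished from others. These points stand. They make remote ratings fewer and the affected children traceable, but they do not mark a late rating in the table.

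Some stronger readings go beyond the text.

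- A reader might infer that remote ratings will be next-day recall. The documents give no call times. Recall is possible, not prescribed.
- A reader might infer that the score may be taken by post. Mail and email are limited to assessments that are not named, so the text neither allows nor excludes it for this item.
- A reader might call Week 2 the only on-treatment subject rating. The Baseline rating also follows an application. Week 2 is the only one after Day 1.
- A reader might expect burning to be under-reported. That is plausible for a brief sensation, but nothing in the documents supports a direction.

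Tolerability also does not rest on this column alone. The Investigator score is planned at Baseline, Week 2 and Week 4.

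**Conclusion.** The point holds as an unresolved conflict between Protocol 7.1.7, footnote e and SAP 10.3 on one side and Appendix 6 on the other. The Week 2 subject tolerability column can mix two kinds of measurement, and the SAP cannot tell them apart.

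The consequence is limited to interpretation. The study has one arm and no inferential statistics, so no error rate is affected, and SAP 10.3 names no change-from-baseline analysis for this score. The shifts in the illustration run from a fraction of a child to just over one child in 20, in either direction. They rest on assumed values of p, k and s. The number of remote Week 2 ratings is not known from the documents.

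The change is still worth making, because tolerability is among the primary endpoints and the correction is cheap.

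**What to change.** In Appendix 6, state that a remote Subject Local Tolerability rating:

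- keeps the 10 to 15 minute interval after that day's scheduled application;
- is taken on a live contact, not by mail or email;
- has its mode, application time and rating time entered in the EDC.

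In SAP 10.3, base the main Week 2 summary on ratings taken within the 10 to 15 minute window. Show any other rating in a separate, flagged listing with its mode and times, so that it is kept but not pooled. Report the number of children in each group.

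The cost is a short addition to each document, a few EDC fields, and some contacts timed to the evening application. The main Week 2 column may lose a few children. The dosing schedule does not change.
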